## 1. PURPOSE OF THE STUDY

---

### a. Brief Summary

Pediatric lower urinary tract symptoms significantly impact children's health as well as their emotional, social, physical, and academic domains due to associated urinary symptoms, lowering their quality of life. Behavioral modifications have been identified as an effective measure to educate children and their families on strategies to rehabilitate the bladder and sphincter function to achieve more sustainable voiding habits and have been shown to reduce pLUTS in 40-70% of patients. Hence, the Bladder Basics was developed as a self-guided digital health platform to provide fun and engaging education on managing pLUTS that patients would receive in a traditional clinical encounter in an accessible manner to patients and their families.

This study is being conducted to understand the retention, engagement, knowledge, behavior change, and user experience among potential Bladder Basics stakeholders.

---

### b. Objectives

This study aims to evaluate the impacts of Bladder Basics on knowledge improvement and clinical symptoms, as well as its acceptability and feasibility through pre-intervention, post-lesson, and post-intervention surveys.

---

### c. Rationale for Research in Humans

This study is being conducted to understand the retention, engagement, knowledge, behavior change, and user experience of potential Bladder Basics stakeholders. We can do this by involving key stakeholders of Bladder Basics.

---

---

## 2. STUDY PROCEDURES

---

### a. Procedures

This is a mixed-methods study of stakeholders such as parents of children ages 5-17. Children will not be surveyed. However, their parents will be asked about their bladder health.

Bladder Basics is designed to be a digital health education tool to improve knowledge of healthy bladder practices. It includes a set of educational videos/lessons to deliver bladder health education on various topics, such as knowing our bladder, why our bladder becomes unhappy, and how to make our bladder happy. In-video activities were also provided to increase learning engagement and facilitate learning. Participants are expected to complete the entire Bladder Basics course within 1 month.

Participants (n=1050) will be recruited using Stanford Medicine Research Office's Research Participation team's services which will include direct emailing, EPIC mychart and social media. Participants who respond to the previously mentioned recruitment methods will be navigated to an online screening survey on REDcap. This survey will assess inclusion and exclusion criteria. If they meet the inclusion criteria, they will be directed to a REDcap consent form. If they meet an exclusion criterion, they will be

informed not to proceed with the study but can leave their contact information for future study opportunities. Further questions may be asked by research personnel via email/call.

Prior to the consent meeting, the research team may reach out to participants by phone to confirm the meeting. If the participant is unable to confirm the meeting by phone, the research team may cancel the meeting and may not be able to reschedule.

After obtaining participants' consent, the virtual Zoom meeting will be recorded and they will be directed to fill out a pre-intervention survey linked to REDCap before accessing Bladder Basics. This survey will collect demographic information and other information, such as knowledge of bladder health practices, children's symptom scores, and self-efficacy as a study baseline.

Once the pre-intervention survey is completed, participants can access Bladder Basics and explore the lessons it offers. After watching each lesson, participants will fill out a post-lesson survey to assess their learning outcomes and/or their experience with Bladder Basics.

Participants will also be asked to complete post-intervention surveys at 4 weeks and 3 months.

All the surveys will be administrated in REDCap.

Section 16 attached the DRA final report, indicating that the risk of ALL the data collected in this study to the University is low.

Main points of the consent will include the following:

- Participation is voluntary
- Participation will have no effect on service/care
- Participants can end participation at any time
- Research staff will never share participants' identity with anyone else (confidentiality will be maintained).
- Patients must complete the consent and HIPAA authorization in order to proceed.

After enrollment, if participants are found to be a repeat participant, have previously enrolled in the study, or have failed to follow study procedures, we will withdraw them from the study. Furthermore, we will stop sending the 4-week and 3-month follow-up survey and will not be able to receive [REDACTED] Amazon gift card. If participants have already been sent the 4-week survey we will proceed with not sending them the 3-month survey and will not receive the [REDACTED] Amazon gift card.

Participants will be notified on their withdrawal via e-mail and access to the Bladder Basics curriculum will be removed.

---

**b. Procedure Risks**

The research team will send interested participants the RedCap consent and survey link or Bladder Basics access link. The consent process for Bladder Basics will be virtual before the participants start the course. The screening and consent language will be readable and inclusive. The surveys will be stored in a HIPAA protected Box folder within 48 hours. The notes will be de-identified. Any analysis will be performed on Stanford-compliant computers.

---

**c. Use of Deception in the Study**

Deception will not be used in this research study.

---

**d. Use of Audio and Video Recordings**

Video recording will occur during the virtual consent meeting after the consent form has been signed. The purpose of the video recording is for our team to identify repeat participants, have evidence showing reasons to pause meetings, and potential IRB review as needed.

All recordings will be stored for our record in HIPAA compliant Stanford Medicine Box. They will not be shown to anyone outside the research team and it will be deleted after the completion of the study according to IRB guidelines.

---

**3. BACKGROUND**

---

**a. Past Experimental and/or Clinical Findings**

Pediatric lower urinary tract symptoms affect 8-22% of school-age children and significantly impact their emotional, social, physical, and academic domains due to associated urinary symptoms, lowering their quality of life. The causes of pLUTS include neurogenic, anatomic, or functional abnormalities that alter typical voiding processes, and the current pLUTS management paradigm ranges from behavioral modifications and pharmaceutical treatment to procedural and surgical intervention. In particular, behavioral modifications aim to educate children and their families on strategies to rehabilitate the bladder and sphincter function to achieve more sustainable voiding habits and have been shown to reduce pLUTS in 40-70% of patients. However, most interventions occur in the clinical setting, leading to lengthy wait times and gaps in care for patients and their families given that pLUTS constitutes up to 40% of pediatric urology clinic visits.

Because of these barriers that impact patient care and clinic resources, the Bladder Basics created through the Stanford Department of Urology in 2021. Bladder Basics is a self-guided digital health platform to increase accessibility of bladder health education to patients and their families. Given that this bladder health digital is one of the first of its kind, this project aims to evaluate the knowledge, behavior change, retention, engagement and user experience of Bladder Basics stakeholders through a mixed methods study.

---

**b. Findings from Past Animal Experiments**

None

---

**4. PARTICIPANT POPULATION**

---

**a. Planned Enrollment**

The total number of participants expected to enroll at all sites is 1050.

---

**b. Age, Gender, and Ethnic Background**

Individuals 18 years and older who are parents or guardians to children aged 5-17 years, of any gender; speaking English; will be recruited for this study.

---

**c. Vulnerable Populations**

We are enrolling parents of children aged 5-17 years. This may also include socio-economically disadvantaged individuals. Standard data protection policies will be observed for all participants and will protect these vulnerable participants: signed consent forms and all paperwork kept in locked cabinets, notes and other data will be stored on Stanford Medicine Box.

---

**d. Rationale for Exclusion of Certain Populations**

Women and minorities will be included in the research study. The study is limited to English-speaking participants due to limited study resources.

---

**e. Stanford Populations**

N/A

---

**f. Healthy Volunteers**

All participants recruited will be self-attested healthy volunteers  $\geq$  18 years of age involved in the care of a child 5-17 years of age.

---

**g. Recruitment Details**

We will partner with the Research Participation team for Honest Broker outreach. Potential participants are identified via STARR and invited by Research Participation team (honest broker) on behalf of study team. See Section 16 for Honest Broker study invitation letters. We will be using Direct Email and Children's Epic MyChart honest broker outreach. For Direct Email, the Research Participation team provides (via secure Box folder) contact info from interested participants to study team. For Epic MyChart, study team receives only the interested responses via Epic MyChart InBasket. Invitations will not be sent to the same individual via more than one honest broker outreach method, unless as a separate reminder. After a patient responds with interest to the honest broker invitation, the study team will respond to the patient via MyChart or Direct Email thanking them for their interest, send our screening survey link that includes a consent and HIPAA Authorization.

We will partner with the Stanford Research Registry to invite potential participants.

We will utilize the prospective tools on STARR to screen patients that meet our inclusion criteria. After generating this STARR cohort, we plan to use EPIC/EMR to further screen patient charts and determine their eligibility. Qualifying patients will be contacted via phone call to assess interest in the study.

Before contacting patients via phone, we will inform all clinicians of our study and obtain permission to cite the provider for their referral so that the patient/participant understands where we received their information from. We will inform providers that we will be screening clinic schedules and reaching out to qualifying patients to assess interest. During the phone call, we will begin by stating that we are contacting them because their doctor referred them to us that they may qualify for our study. Permission has been obtained and documented; attached in Section 16.

We also plan to use social media for study recruitment. We will turn off comments on any public social media posts. We will set up our social media (e.g., Facebook) page so that the security settings do not allow participants or others from the public to post on the wall. They will only be able to send messages via social media (e.g., Facebook). This is so that they are not posting private information or PHI on the publicly viewed wall. We may also post our screening survey on our PI's research lab website to enhance participant recruitment.

Parents may also be approached to be a part of the study at the time of referral to the clinic. Snowball sampling may also be employed. A screening survey will be conducted before selecting parents for interviews.

In addition, IRB-approved flyers will be posted in the clinic or around campus, passively in public spaces, in PCHA pediatric practices and external clinics with site permission, on our lab website, on the Stanford research websites such as those listing current research, Urology clinic website/webpage in Stanford Children's Hospital, and dispersed at health fairs/public events.

We also plan to recruit on virtual platforms, such as e-newsletters.

Lastly, we also may use the patient access service center (PASC) to recruit participants.

This study is an alternative to a clinical program that Pediatric Urology offers called Bladder Bootcamp (BBC); scheduling for BBC is done by PASC. We are interested in offering our study to patients who are waiting to be seen for their first visit at LPCH (Bladder Bootcamp or new patient visit). In terms of using PASC, we may ask PASC to direct patients to our website to learn more about our study or ask patients if it is okay for our research team to contact them about the study.

Once potential participants express interest from the above recruitment methods, we send them the link to a REDcap web questionnaire (screening survey) to determine their eligibility for the study. If they meet all the inclusion criteria, they can proceed to complete an electronic consent form, also through REDcap. If they meet the exclusion criteria, they will be informed not to proceed with the study but can leave their contact

information for future study opportunities. Further questions may be asked by research personnel via email/call. The consent form will be administered through REDcap as a form – participants are asked to read the form and provide an electronic signature at the end of the consent form on REDcap. Once we have their consent, we proceed with sending the REDCap pre and post survey.

---

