#### **i. Screening Procedures**

We are recruiting by advertising our flyer and recruitment messages on virtual platforms, such as e-newsletters. On these flyers, we tell interested participants to contact us at our lab email. Flyers will also be posted in the clinic or around campus, in pediatrician offices within the Stanford network, on our lab website, and on the Stanford research websites such as those listing current research and Urology clinic website/webpage in Stanford Children's Hospital.

We are also recruiting using the honest broker system at Stanford – through MyChart messages and Direct Email.

We will contact patients via phone to assess interest, with permission from their provider to cite them as a referral so that patients understand where we obtained their information.

We will use social media to recruit potential participants

Parents may also be approached to be a part of the study at the time of referral to the clinic.

Lastly, we may use the patient access service center (PASC) to recruit participants and offer our study to patients who are waiting to be seen for their first visit at LPCH (Bladder Bootcamp or new patient visit). In terms of using PASC, we may ask PASC to direct patients to our website to learn more about our study or ask patients if it is okay for our research team to contact them about the study.

Once they express interest from the above recruitment methods, we send them the link to a REDcap web questionnaire (screening survey) to determine their eligibility for the study. If they meet all the inclusion criteria, they can proceed to complete an electronic consent form, also through REDcap. If they meet the exclusion criteria, they will be informed not to proceed with the study but can leave their contact information for future

study opportunities. Further questions may be asked by research personnel via email/call. The consent form will be administered through REDcap as a form – participants are asked to read the form and provide an electronic signature at the end of the consent form on REDcap. Once we have their consent, we proceed with sending the REDCap pre and post survey.

---

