# Impact, Feasibility, and Acceptability of a Digital Health Intervention for Healthy Children With Pediatric Lower Urinary Tract Symptoms (pLUTS)

## Statistical Analysis Plan

NCT05852353

July 14, 2025

Planned sample size was 100 enrolled parent-child dyads. The final sample included 70 parent-child dyads.

Feasibility metrics, secondary outcomes, and sociodemographic data were analyzed descriptively. For both the overall group and sub-groups, the following statistics will be calculated: count, percentage, mean scores, standard deviation (SD), median scores, interquartile range (IQR), minimum and maximum scores.

Paired t-tests were used for normally distributed variables, while non-parametric tests were used (Wilcoxon and Sign) for non-normally distributed variables to compare pre- and post- intervention scores. McNemar's test was used for categorical variables to evaluate changes in proportions from baseline to post-intervention.

Missing data was addressed using complete-case analysis; participants were only included if they completed the surveys specific to each post-intervention timepoint.

Statistical significance was set at  $p < 0.05$ , and analyses were conducted using R.

The reliability of the survey measuring acceptability and education design was assessed using Cronbach's alpha with an  $\alpha \geq 0.6$  and  $\leq 0.8$  considered acceptable internal consistency. Bar charts were generated to visualize the distribution of Likert scale responses, offering further insight into response patterns and helping to further explain the reliability test results.

A hybrid process combining inductive and deductive thematic analysis, guided by the theoretical framework of acceptability, was performed by two research team members to analyze open-ended feedback on families' experiences and perceptions of Bladder Basics. SPSS and Dedoose were used for statistical and thematic analyses, respectively.

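### Some families are to be recruited while awaiting or entering urology care, and no plan to record that care is described, so symptom and knowledge changes, especially at 3 months, can mix Bladder Basics with clinic education and treatment

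*Protocol*

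**What the plan says.** **Recruitment.** Protocol section 4.g lists many routes. Several reach families who are entering urology care. On the patient access service center it says "We are interested in offering our study to patients who are waiting to be seen for their first visit at LPCH", and names Bladder Bootcamp and the new patient visit as the visits meant. Section 4.i repeats the plan to "offer our study to patients who are waiting to be seen for their first visit at LPCH". Section 4.g also allows an approach at the point of referral, and contact with patients found by screening clinic schedules.

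**Relation to clinic care.** Section 4.g states: "This study is an alternative to a clinical program that Pediatric Urology offers called Bladder Bootcamp (BBC". The consent points in section 2.a say "Participation will have no effect on service/care". Section 1.a describes Bladder Basics as giving "education on managing pLUTS that patients would receive in a traditional clinical encounter".

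**Eligibility.** Section 4.h admits adult English-speaking parents or guardians of a child aged 5 to 17, with or without bladder problems. Its exclusions do not mention bladder care of any kind.

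**Follow-up and data.** Section 2.a: "Participants will also be asked to complete post-intervention surveys at 4 weeks and 3 months". It describes the baseline survey as demographics plus an open-ended list of examples: knowledge, the child's symptom scores and self-efficacy. Other bladder care is not among them.

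**Analysis.** The SAP uses paired t, Wilcoxon, sign and McNemar tests of change from baseline. On missing data it says "participants were only included if they completed the surveys specific to each post-intervention timepoint". It gives no comparator and no adjustment or sensitivity analysis for other care. Sub-groups are mentioned but not defined.

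**The concern.** Section 1.b sets out to evaluate the impact of Bladder Basics on knowledge and clinical symptoms. For a family enrolled from a waiting list, the booked visit comes after baseline. If it takes place before the 3-month survey, the parent's knowledge and the child's symptom score at that survey also carry the effect of the visit and of any treatment begun there. The SAP would count all of this as change after Bladder Basics.

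This is narrower than the general weakness of a single-group comparison. Maturation, regression to the mean and repeat testing leave no date in the data. A clinic visit does, so the assessments made before and after it can be told apart, but only if somebody collects the date.

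**Working it through.** **1. The passages side by side.**

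| Element | Where | What it gives |
|---|---|---|
| Families about to enter care are sought | Protocol 4.g, 4.i | Yes, as optional routes among many |
| Competing care is of the same kind | Protocol 1.a | Yes, the same education |
| Such care bars entry | Protocol 4.h | No |
| Participants put off or give up the visit | Protocol 4.g, 2.a | Not stated |
| Time for a visit to occur | Protocol 2.a, 4.l | 4 weeks, then 3 months |
| Other care is recorded | Protocol 2.a | No plan described; list of examples is open |
| Other care is handled in the analysis | SAP | No |
| Waiting time for clinic | Protocol 3.a | Called lengthy; no figure |
| Share seen before each survey | neither document | Not given |

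The first eight rows are enough for mixing to be possible. The last means its size cannot be calculated.

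**2. Illustration of what the missing share could do.** The plan has no figure of its own on this point to reproduce.

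Inputs from the documents:
- n = 70 dyads (SAP, final sample)
- significance at p < 0.05 (SAP), taken here as two-sided
- response to behavioral modification r = 40% to 70% (Protocol 1.a and 3.a)

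Assumptions not in the documents:
- a yes/no symptom outcome
- all 70 children symptomatic and assessed at 3 months
- no effect of Bladder Basics
- a share s of families seen before the 3-month survey
- background change b of 5% to 20% in each direction

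Exact McNemar test with nobody worsening: p = 2 × 0.5^k for k improvers.
- k = 5: 2 × 0.5^5 = 0.0625
- k = 6: 2 × 0.5^6 = 0.031

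Share seen at which clinic care alone gives 6 expected improvers: 6/(70 × 0.70) = 12.2%, or 6/(70 × 0.40) = 21.4%. Six is only the expected number. With no background change, the chance of actually reaching 6 or more at that share is 56%.

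Allowing background change, P(improve) = s·r + (1 − s·r)·b and P(worsen) = (1 − s·r)·b. Summing the exact test over all outcomes gives the chance of a significant improvement that owes nothing to Bladder Basics:

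| Share seen before 3 months | Chance, n = 70 |
|---|---|
| 0% | 0.8% to 1.5% |
| 10% | 5% to 21% |
| 20% | 12% to 65% |
| 30% | 25% to 92% |
| 50% | 59% to 99.9% |

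Each range covers r = 40% to 70% and b = 5% to 20%.

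If only half the dyads (35) are symptomatic and assessed, the same formulas give 12% to 57% at a 30% share. The answer therefore runs from negligible to decisive, depending on inputs that the documents do not supply.

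**3. Direction.** Care between baseline and a survey, if it helps, enlarges the apparent gain. Care before baseline may already have raised knowledge or reduced symptoms, which leaves less room for change. The net direction is not fixed.

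**The case against.** The strongest reply is that the exposure may be small.
- The waiting-list route is optional and stands beside direct email, a research registry, social media, flyers and newsletters. Children without bladder problems are eligible. Nothing shows that any enrolled family came by this route.
- If waits are long, many visits may fall after the 3-month survey.
- The survey list is open and the instruments are not in the documents, so a question on other care may exist.
- The illustration rests on a yes/no symptom endpoint that the documents never define; section 2.a collects scores. A rate at which behavioral modification reduces symptoms is also not a rate of crossing from symptomatic to symptom-free.

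All of this stands, and it limits the point to what can happen. It does not remove it, since no passage keeps recruited families out of clinic care, and even if a survey item exists the SAP makes no use of it.

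Three stronger readings are tempting and are not supported:
- A reader might infer that the symptomatic part of the sample comes mainly from booked patients, or that the results are known to be contaminated. The documents give no such breakdown.
- A reader might infer that the bias must favour Bladder Basics. Care before baseline could work the other way.
- A reader might see a contradiction between calling the study an alternative to Bladder Bootcamp and assuring families that care is unaffected. Both can be true, if the first describes the kind of programme and the second the family's entitlement. The wording needs clarifying, no more.

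**Conclusion.** The point holds as one of attribution. The plan seeks some families who are about to receive similar education or treatment, follows them for 3 months, describes no record of that care, and tests change without a comparator. Observed change in symptoms and knowledge can therefore include clinic care. The risk is likely greater at 3 months than at 4 weeks, because more time has passed, although a booked visit can also fall within 4 weeks.

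The size is unknown. The percentages above are illustrations that rest on the stated assumptions and are not estimates for this trial. The conclusion itself needs only the recruitment, eligibility, follow-up and analysis passages.

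**What to change.** 1. **Record the care.** Add one item to the baseline, 4-week and 3-month surveys asking the type and date of any urology visit, Bladder Bootcamp attendance or bladder treatment. The SAP already reports a final sample of 70, so for dyads already enrolled take the dates from the chart where the authorization allows. The protocol describes chart access only for screening, so this must be checked, and families treated elsewhere would be missed.
2. **Use it in the SAP.** Keep the comparison in all completers and label it change under Bladder Basics plus any usual care. Report how many families had such care before baseline and before each timepoint. Add a sensitivity analysis limited to assessments made before any such care since baseline. It should not become the main comparison: being seen is a post-baseline event related to severity, so the subset may hold milder cases.
3. **If dates cannot be obtained,** report the change, particularly at 3 months, as not separable from clinic care, and do not attribute it to Bladder Basics alone.
4. **Clarify Protocol 4.g.** State whether participants still attend a booked visit or Bladder Bootcamp, in terms consistent with the consent assurance in section 2.a.

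The cost is one survey item or a chart look-up, some SAP wording, a smaller and possibly selected subset in the sensitivity analysis, and a more cautious 3-month conclusion. The subset still has no control group, so regression to the mean, maturation and repeat testing remain.
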